1. PROTOCOL SUMMARY

1.1 SYNOPSIS

Title: Full title: A randomized, double-blind, placebo-controlled, clinical trial of a 3-dose, 28-day regimen of PfSPZ Vaccine in healthy, adult participants to determine safety, tolerability and efficacy against heterologous *Plasmodium falciparum* controlled human malaria infection conducted 3 and 12 weeks after immunization

Sponsor's Protocol Number: USSPZV7

Study Description and Rationale: USSPZV7 is a randomized, double-blind, placebo-controlled trial of Sanaria® PfSPZ Vaccine administered on Days 1, 8 and 29 by direct venous inoculation (DVI) to assess safety, tolerability, immunogenicity, and vaccine efficacy (VE) against heterologous controlled human malaria infection (CHMI) with the 7G8 clone of *Plasmodium falciparum* (Pf) conducted at 3 or 12 weeks after the third immunization. The trial is designed to determine if individuals living in a non-malaria endemic area such as the United States (US) are protected against heterologous CHMI conducted at these time points. Enrollment will target at least 50% women due to the importance of collecting data relevant to women of child-bearing potential in Africa, for whom Pf malaria is a serious cause of morbidity and mortality during pregnancy. A companion trial taking place in malaria-naïve Indonesian soldiers will assess the same regimen for safety, tolerability, immunogenicity, and VE against naturally transmitted Pf malaria in Indonesian West New Guinea. Together, the two trials will provide a direct bridge between VE against CHMI and VE against naturally transmitted malaria in malaria-naïve individuals, a first in the history of malaria vaccine development.

The regimen for the USSPZV7 trial is based on a prior study (MAVACHE) where the day 1, 8 and 29 immunization regimen protected 5/6 non-malaria immune German adults against heterologous CHMI at 3 weeks after the last vaccination and 5/6 different German adults against heterologous CHMI 9-10 weeks after the last vaccination and 6-7 weeks after an initial homologous CHMI. The use of a heterologous strain for CHMI (heterologous meaning different from the vaccine strain) increases the stringency of the CHMI by introducing variant antigens and epitopes. When naturally transmitted malaria in Mali, and CHMI in the US, were used to measure VE, protection in the field over 24 weeks was as good as or better than protection against heterologous CHMI conducted at 24 weeks using exactly the same regimen¹, indicating the stringency of heterologous CHMI and its ability to conservatively estimate field protection (Silva, *Nature Communications*, 2022).

¹ In the first pair of bridging studies (Warfighter 1 trial in the US and MLSZPV1 trial in Mali), the regimen was 2.7×10^5 PfSPZ administered by DVI weeks 0, 4, 8, 12 and 20; in the second pair of bridging studies (Warfighter 2 trial in the US and MLSZPV2 trial in Mali), the regimen was 1.8×10^5 PfSPZ administered weeks 0, 8 and 16. In these paired studies, VE over 24 weeks of surveillance was as good or better in Mali (field transmission) than in the USA (24 week heterologous CHMI using Pf7G8). References: Warfighter 1 [1], MLSZPV1 [2], Warfighter 2 [3], MLSZPV2 [4].

To provide additional data on VE to support PfSPZ Vaccine licensure in the US, EU, Indonesia and African countries, several companion trials are assessing VE against naturally transmitted malaria in Indonesia (see above), African women of child-bearing potential (MLSPZV4), African children 6 to 9 years of age (MLSPZV5) and African women who are pregnant (MLSPZV6). In combination, these several trials are designed to provide data supporting the use of PfSPZ Vaccine to protect three important vulnerable groups: malaria-naïve travelers, children and pregnant women. In the latter case, vaccine can be administered prior to pregnancy (MLSPZV4) or during pregnancy (MLSPZV6). The pregnancy indication includes malaria-naïve women as well as malaria-exposed women, as the former have limited options for chemoprophylaxis when traveling to malaria-endemic areas.

The TravSPZV trial replaces the 9-10 week interval to CHMI used in the MAVACHE trial in Germany with two intervals (3 weeks, 12 weeks), to represent a duration of travel for a typical traveler to a malaria endemic area. Twelve weeks is an interval that encompasses most of the international travel to such areas. The Warfighter 3 trial is being conducted in the US at the current time and is providing preliminary estimates of VE against heterologous CHMI at 2, 6 and 10 weeks; USSPZV7 will be adding two additional timepoints to these data; 3 and 12 weeks.

USSPZV7 will be conducted at the University of Maryland at Baltimore's Center for Vaccine Development and Global Health (UMB CVD).

Objectives:**Primary Objective:**

1. To measure the combined vaccine efficacy (VE) of PfSPZ Vaccine against Pf malaria (parasitemia) following heterologous parenteral CHMI with PfSPZ Challenge (7G8) administered 3 and 12 weeks after last dose of vaccine, in the modified intention-to-treat (mITT) population.
2. To assess the safety and tolerability of PfSPZ Vaccine administered as 3 doses of 9.0×10^5 PfSPZ on days 1, 8 and 29.

Secondary Objective:

1. To measure VE separately at each CHMI timepoint (3 and 12 weeks after V3).
2. To measure antibody responses to PfCSP following vaccination and determine if they are correlated with protection.

Exploratory Objectives:

1. To compare VE between groups with CHMI 3 or 12 weeks after V3.
2. To measure VE in the ITT and ATP populations.
3. To measure VE using time-to-event analysis.
4. To measure antibody responses to other Pf antigens and to PfSPZ and determine if they are correlated with protection.
5. To measure the ability of antibody responses to inhibit sporozoite invasion of hepatocytes and determine if the percent inhibition is correlated with protection.
6. To measure cellular immune responses following immunization and determine if they are correlated with protection.
7. To analyze innate and adaptive immune system states before and at early time-points after vaccination by using: 1) RNA-seq profiling of whole blood/PBMC; 2) immune phenotyping of single cells using flow cytometry

and CITE-seq; and 3) profiling of circulating proteins and metabolites. The objective of this exploratory goal is to search for biomarkers of vaccine induced humoral and cellular immune responses and protection.

8. To deep sequence the peripheral immune repertoire of cells to assess the cell receptor frequencies.

Endpoints:**Primary Endpoint:**

1. VE computed as one minus the estimated risk ratio for Pf malaria (parasitemia) detected by PCR beginning 7 days after CHMI up to 28 days in the modified intention to treat population (proportional efficacy analysis) combining data across the two CHMI timepoints.
2. The differences in proportions of vaccinees compared to controls experiencing related moderate, severe, or serious solicited and unsolicited adverse events and laboratory abnormalities after vaccination.

Secondary Endpoints

1. VE as above, for each timepoint.
2. Antibody levels to PfCSP measured by ELISA comparing vaccinees to controls, and protected (no parasitemia occurring post CHMI) to non-protected (parasitemia occurring post CHMI) vaccinees.

Exploratory Endpoints:

1. VE as above.
2. VE as above.
3. VE computed as one minus the estimated hazard ratio.
4. Investigation of any differences in outcome based on gender, race or ethnicity.
5. Antibody levels to whole PfSPZ by automated immunofluorescence assay (IFA) and/or by other assays to be further defined, which may include assays to assess responses to multiple Pf antigens, antibody subclass assays and functional assays, comparing vaccinees to controls, and protected (no parasitemia occurring post CHMI) to non-protected (parasitemia occurring post CHMI) vaccinees.
6. Capacity to inhibit sporozoite invasion of hepatocytes (HC-04 cells) in vitro by inhibition of sporozoite invasion (ISI) assay comparing vaccinees to controls, and protected (no parasitemia occurring post CHMI) to non-protected (parasitemia occurring post CHMI) vaccinees.
7. Cellular immune responses to whole PfSPZ and synthetic peptides from selected Pf antigens by intracellular cytokine staining (ICS)/ flow cytometry and/or other assays to be defined comparing vaccinees to controls, and protected (no parasitemia occurring post CHMI) to non-protected (parasitemia occurring post CHMI) vaccinees.
8. RNA transcriptome quantification as detected by RNA-seq and protein levels in serum, and serum analyte analysis, comparing vaccinees to controls, and protected (no parasitemia occurring post CHMI) to non-protected (parasitemia occurring post CHMI) vaccinees.
9. Deep sequencing of immune receptor genes.

Methodology

This will be a randomized, double-blind, placebo-controlled trial conducted at a single site as described above. Participants will be randomized to PfSPZ Vaccine

(vaccinees) or normal saline (NS) placebo (controls) in a 3:1 assignment ratio. PfSPZ Vaccine and NS injectates are prepared as clear, non-viscous, odor-free solutions that cannot be distinguished by the administrator or by the recipient, facilitating a double-blind design. Randomization will be done online using software provided by data management.

There will be 45 vaccinees and 15 controls. The reasons for the 3:1 imbalance are to: 1) collect more information on adverse events associated with vaccine administration, and 2) optimize the numbers to assess vaccine efficacy (VE) in the CHMI model. Participants who complete all immunizations will receive a total of 2.7×10^6 PfSPZ. In prior studies, single doses of 2.7×10^6 PfSPZ have been well tolerated in non-immune adults and there has not been any evidence that repeat dosing leads to increasing side effects. Therefore, 3 doses of 9.0×10^5 PfSPZ has been shown to be very safe and well tolerated.

Table 1. USSPZV7 Study Design

Groups	n	PfSPZ Vaccine dose (# PfSPZ)	Total PfSPZ over 3 doses (# PfSPZ)	Immunization (Days)			Weeks to CHMI	PfSPZ Challenge (7G8) dose (# PfSPZ)
				1	8	29		
1 -PfSPZ Vaccine	45	9.0×10^5	2.7×10^6	x	x	x	x	3.2×10^3
2 -NS* controls	15	0	0	x	x	x	x	3.2×10^3
Total # of participants: 60								

* normal saline placebo

VE will be assessed 3 and 12 weeks after last immunization by exposure to PfSPZ Challenge (7G8), which is composed of aseptic, purified, cryopreserved infectious PfSPZ cloned from a Pf strain isolated in Brazil, and thus heterologous to the vaccine, which is derived from strain PfNF54 originating in West Africa. As with immunization, the PfSPZ will be administered by direct venous inoculation (DVI). Participants will be followed intensively for 4 weeks after CHMI to determine CHMI outcome and then for an additional 4 weeks until last study visit. Parasitemia following CHMI will be measured by highly sensitive quantitative polymerase chain reaction (qPCR). Protection will be defined as absence of parasitemia as detected by qPCR during the 28 days following injection of 3.2×10^3 PfSPZ of PfSPZ Challenge (7G8).

Statistical Methods

The primary outcome for these studies will be VE measured as $[1 - \text{risk ratio}] \times 100$. The outcomes of both CHMI's will be combined. Sample sizes of 45 and 15 for the vaccine and placebo groups were selected to be able to show with 83% power, if there are six drop-outs from the vaccine group and two from the control group prior to CHMI, that an infection rate of 92.3% in the controls (12/13 developing parasitemia) and 51% in the vaccinees (20/39 developing parasitemia) is statistically significantly different ($\alpha=0.05$, 2-tailed) (VE=44.4%). As we expect VE to be higher than this, the sample size should be adequate.

Regarding safety, the study provides the following power to identify adverse outcomes:

1. If no PfSPZ Vaccine-related SAEs are observed, the sample size of 45 provides 95% confidence that the true rate of SAEs caused by immunization is less than 6.7%, 90% confidence that the true rate of SAE's is less than 5.0%, 85% confidence that the true rate of SAEs is less than 4.2%, and 80% confidence that the true rate of SAEs is less than 3.5%.

With regard to the ability to make comparisons between vaccinees and placebo recipients in the rates of grade 2 and grade 3 adverse events, where significant differences might indicate poor tolerability, a sample size of 45 vaccinees and 15 placebo recipients will show a statistically significant difference ($p<0.05$, two-tailed) between 10/45 vaccinees experiencing poor tolerability on the one hand, and 0/15 controls on the other hand.

Phase:	Phase I
Estimated Number of Participants Screened:	240 (4:1)
Estimated Number of Participants Enrolled:	60 healthy adults (males or non-pregnant females), 18-50 years of age (45 vaccinees, 15 placebo controls); a target of 50% women
Description of Sites/Facilities Enrolling Participants:	1. University of Maryland at Baltimore's Center for Vaccine Development and Global Health
IND Sponsor:	Sanaria Inc.
Name of Investigational Product:	Vaccine test product: Sanaria® PfSPZ Vaccine (NF54) Product used to conduct CHMI: Sanaria® PfSPZ Challenge (7G8)
Description of Study Intervention:	The vaccine consists of radiation-attenuated, aseptic, purified sporozoites (SPZ) cryopreserved in liquid nitrogen vapor phase (LNVP) at -150° to -196°C. PfSPZ Vaccine is diluted in phosphate buffered saline (PBS) with human serum albumin (HSA) to achieve the correct dosage and is administered by DVI. PfSPZ Challenge (7G8) is similar but has not been attenuated by radiation and is therefore infectious. PfSPZ Vaccine is composed of PfSPZ derived from the NF54 strain of Pf, which is thought to be from West Africa, and PfSPZ Challenge (7G8) is composed of PfSPZ derived from the 7G8 clone of Pf, which is from Brazil.

Safety Monitoring

Solicited and unsolicited adverse events will be collected at specified intervals during the trial. In addition, laboratory testing (complete blood count, creatinine level, alanine aminotransferase level) will be conducted periodically during the trial. Serious adverse events (SAEs) will be recorded from the time of first vaccination to the end of the trial. Halting rules are defined in the protocol (e.g., the occurrence of an SAE deemed related to the vaccine).

There will be a Safety Monitoring Committee (SMC) to provide independent safety oversight. The SMC will consist of senior physicians with expertise in the conduct of clinical trials including a Local Safety Monitor. Membership will be restricted to individuals without conflicts of interest. The SMC will be scheduled to meet prior to the start of the study or early in the course of the trial to review the SMC Charter and the details of the clinical trial, again at the time of study close-out. Other SMC meetings will be scheduled on an “as needed” basis to address any safety concerns that may arise.

Study Duration:

The entire study will take approximately 12 months to complete, including 3 months of recruitment. The period of follow-up for each immunized participant and placebo control is through 8 weeks post-CHMI.

Participant Duration:

Participation will last up to 24 weeks (not including screening) for those undergoing CHMI at 12 weeks and 15 weeks (not including screening) for those undergoing CHMI at 3 weeks.

[figure not shown]
Study Period:

Estimated date first participant screened: October, 2022.

Estimated date first participant immunized: November, 2022.

Estimated date last study visit of last study participant: July, 2023.

1.2 SCHEMA

1.3 SCHEDULE OF ACTIVITIES

The detailed schedule of events outlining the procedures to be performed at each study visit and participant contact is provided in **Table 3**.

Table 3. Schedule of Activities

3 week CHMI		Screen	Day -7	1	8	10	15	29	31	38	43	50	57	58	59	60	61	62	63	64	65	66	67	68	70	72	75	78	106	
Study Day			Day -90 to Day -1	+/- 7	+/- 3	+/- 3	+/- 5	+/- 2	+/- 3	+2	+/- 2	+/- 5	+/- 5	-	-	-	-	-	-	-	-	-	-	+/- 2	+/- 2	+/- 7	+/- 10			
Windows																														
Visit Number			1	2	3	4	5	6	7	8	9	10	11	12	13	14	15	16	17	18	19	20	21	22	23	24	25	26	27	28
Time Interval		Scr ¹	-7	Imm1	Imm2	+2	+7	Imm3	+2	+7	+14	CHMI	+7	+8	+9	+10	+11	+12	+13	+14	+15	+16	+17	+18	+20	+22	+25	+28	+56	
Informd Consent		X																												
Eligibility Criteria Review		X	X	X	X				X				X																	
Medical History/Update		X	X	X	X	X	X	X	X	X	X	X	X	X	X	X	X	X	X	X	X	X	X	X	X	X	X	X		
Physical Examination ²		X	X	X	X	X	X	X	X	X	X	X	X	X	X	X	X	X	X	X	X	X	X	X	X	X	X	X		
Vital Signs (BP, HR, temperature)		X	X	X	X	X	X	X	X	X	X	X	X	X	X	X	X	X	X	X	X	X	X	X	X	X	X	X		
CBC with differential	EDTA	4	4	4			4		4	4	4																		4	
Serum chemistry ³	SST	8.5		8.5			8.5					8.5	8.5																8.5	
HIV ELISA, HBsAg, anti-HCV	SST	3.5																												
COVID-19 PCR (if clinically indicated)			X																											
EKG		X																												
Urine β HCG ⁴		X		X	X			X				X																		
Immunization				X	X			X																						
Provision /Review of Memory Aid				X	X	X	X	X	X	X	X	X	X	X	X	X	X	X	X	X	X	X	X	X	X	X	X	X		
Telephone Follow Up											X																			
CHMI													X																	
qPCR ⁵		2													2	2	2	2	2	2	2	2	2	2	2	2	2	2	2	2
Adverse Events / Clinical Events					X	X	X	X	X	X	X	X	X	X	X	X	X	X	X	X	X	X	X	X	X	X	X	X		
SAEs					X	X	X	X	X	X	X	X	X	X	X	X	X	X	X	X	X	X	X	X	X	X	X	X		
Concomitant Medications		X	X	X	X	X	X	X	X	X	X	X	X	X	X	X	X	X	X	X	X	X	X	X	X	X	X	X		
IMMUNOASSAYS																														
Serum (antibodies)	SST		25	0			25		0		25	25	0	0	0	0	0	0	0	0	0	0	0	0	0	0	0	0	0	25
Immune regulation	PAXgene		1						1				1																	
PBMCs (cellular immunology, immune regulation)	EDTA		60	0			50		50		50	50	30	0	0	0	0	0	0	0	0	0	0	0	0	0	0	0	0	
Daily volume (mL)			16	92	12.5	0	0	75	0	55	0	87.5	87.5	33	2	2	2	2	2	2	2	2	2	2	2	2	2	2	39.5	0
Cumulative blood volume (mL)			16	108	121	121	121	196	196	251	251	338	426	459	461	463	465	467	469	471	473	475	477	479	481	483	485	487	526	526

¹ Screening Visit also includes Assessment of Understanding, Cardiovascular Risk Assessment, height, weight and BMI measurements

² Physicals will be performed during screening. All other physicals will be performed if indicated by medical history

³ Screening serum chemistry: glucose, creatinine, ALT, AST, serum chemistry at all other time points: ALT and creatinine

⁴ Serum β HCG may be substituted

⁵ If a subject is diagnosed with malaria infection, the following samples will be drawn prior to initiation of treatment: CBC w/diff (4mL), Chemistry (5mL), sample for TBS (2mL), sample for UWash PCR (2mL). This will add an additional 13 mL to the cumulative blood volume. qPCR will be performed 28 days post CHMI if subject remains malaria negative. Blood draw for qPCR will be discontinued upon malaria diagnosis and treatment.

12 week CHMI		Screen	Day -7	1	8	10	15	29	31	38	43	113	120	121	122	123	124	125	126	127	128	129	130	131	133	135	138	141	169
Study Day		Day -90 to Day -1	+/- 7	+/- 3	+/- 3	+/- 5	+/- 2	+/- 3	+2	+/- 2	+/- 5	+/- 5	-	-	-	-	-	-	-	-	-	-	-	+/- 2	+/- 2	+/- 7	+/- 10		
Windows		1	2	3	4	5	6	7	8	9	10	11	12	13	14	15	16	17	18	19	20	21	22	23	24	25	26	27	28
Visit Number		Scr ¹	-7	Imm1	Imm2	+2	+7	Imm3	+2	+7	+14	CHMI	+7	+8	+9	+10	+11	+12	+13	+14	+15	+16	+17	+18	+20	+22	+25	+28	+56
Inform ed Consent		X																											
Eligibility Criteria Review		X	X	X	X				X			X																	
Medical History/Update		X	X	X	X	X	X	X	X	X	X	X	X	X	X	X	X	X	X	X	X	X	X	X	X	X	X		
Physical Examination ²		X	X	X	X	X	X	X	X	X	X	X	X	X	X	X	X	X	X	X	X	X	X	X	X	X	X		
Vital Signs (BP, HR, temperature)		X	X	X	X	X	X	X	X	X	X	X	X	X	X	X	X	X	X	X	X	X	X	X	X	X	X		
CBC with differential	EDTA	4	4			4		4	4	4																		4	
Serum chemistry ³	SST	8.5		8.5			8.5			8.5	8.5																	8.5	
HIV ELISA, HbSAg, anti-HCV	SST	3.5																											
COVID-19 PCR (if clinically indicated)		X																											
EKG		X																											
Urine β HCG ⁴		X		X	X			X			X																		
Immunization			X	X				X																					
Provision /Review of Memory Aid			X	X	X	X	X	X	X	X	X	X	X	X	X	X	X	X	X	X	X	X	X	X	X	X			
Telephone Follow Up									X																				
CHMI												X																	
qPCR ⁵		2														2	2	2	2	2	2	2	2	2	2	2	2	2	
Adverse Events / Clinical Events			X	X	X	X	X	X	X	X	X	X	X	X	X	X	X	X	X	X	X	X	X	X	X	X			
SAEs			X	X	X	X	X	X	X	X	X	X	X	X	X	X	X	X	X	X	X	X	X	X	X	X			
Concomitant Medications		X	X	X	X	X	X	X	X	X	X	X	X	X	X	X	X	X	X	X	X	X	X	X	X	X			
IMMUNOASSAYS																													
Serum (antibodies)	SST	25	0			25	0	0	25	25	0	0	0	0	0	0	0	0	0	0	0	0	0	0	0	0	0	25	
Immune regulation	PA Xgene	1						1				1																	
PBMCs (cellular immunology, immune regulation)	EDTA	60	0			50	0	50		50	50	30	0	0	0	0	0	0	0	0	0	0	0	0	0	0	0		
Daily volume (mL)		16	92	12.5	0	0	75	0	55	0	87.5	87.5	33	2	2	2	2	2	2	2	2	2	2	2	2	2	39.5	0	
Cumulative blood volume (mL)		16	108	121	121	121	196	196	251	251	338	426	459	461	463	465	467	469	471	473	475	477	479	481	483	485	487	526	526

¹ Screening Visit also includes Assessment of Understanding, Cardiovascular Risk Assessment, height, weight and BMI measurements² Physicals will be performed during screening. All other physicals will be performed if indicated by medical history³ Screening serum chemistry: glucose, creatinine, ALT, AST, serum chemistry at all other time points: ALT and creatinine⁴ Serum β HCG may be substituted⁵ If a subject is diagnosed with malaria infection, the following samples will be drawn prior to initiation of treatment: CBC w/diff (4mL), Chemistry (5mL), sample for TBS (2mL), sample for UWash PCR (2mL). This will add an additional 13 mL to the cumulative blood volume. qPCR will be performed 28 days post CHMI if subject remains malaria negative. Blood draw for qPCR will be discontinued upon malaria diagnosis and treatment.

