The WHO Consensus Document for the Standardization of Design and Conduct of *P. falciparum* Sporozoite Challenge Trials [61] will be utilized to help ensure the safety of all participants from the day of CHMI until completion of all post-CHMI follow-up.

The clinical study team will review each participant's adherence to the schedule and safety follow-up to date. This review will be done to identify any likelihood that the participant may be unreliable or non-compliant with study visits post-challenge. A participant who has been non-compliant with prior study visits may be excluded from the CHMI phase and followed for safety. Prior to CHMI, at least 1-2 emergency contact numbers will be confirmed and verified as authentic for each participant.

Study participants will be counseled at the time of challenge about the signs and symptoms of malaria and given 24 hour/day contact information should any signs or symptoms develop. Participants will have daily PCR done beginning 7 days after PfSPZ Challenge until 18 days post-CHMI. If symptoms are present, a blood sample for PCR may be obtained outside the window of scheduled samples. Those participants that do not develop parasitemia will have follow-up visits on +20, +22, +25 and +28 days post CHMI. A

confirmatory negative PCR will be documented on all participants at Day 28 post CHMI. All participants will be seen for their final visit on 56 days post CHMI.

As soon as malaria infection is documented, the participant will be treated; prompt treatment minimizes the risk of developing a serious complication due to the malaria infection. Complaints such as chest pain, palpitations, or shortness of breath are not uncommon in individuals with malaria. Nonetheless, the report of these symptoms by a participant will prompt a clinical evaluation by one of the investigators, and may include the consultation of a cardiologist. If a participant's symptoms are consistent with or suspicious for a cardiac etiology, patient care will be expedited and will be in accordance with the current American College of Cardiology/ American Heart Association clinical practice guidelines.

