8.1.5 CONTROLLED HUMAN MALARIA INFECTION

CHMI with cryopreserved, aseptically prepared vialled infectious Pf sporozoites from the 7G8 clone (PfSPZ Challenge (7G8)) will occur by direct venous inoculation.

Prior to CHMI, the following activities and procedures will be performed:

- Inclusion and exclusion criteria will be reviewed
- Medical history, AEs and SAEs will be updated to include concomitant medications, a directed physical examination will be performed (if indicated), and vital signs will be recorded
- Results of pregnancy test (urine or blood β -HCG) will be confirmed. CHMI will not proceed unless a negative pregnancy test has been obtained within 24 hours of CHMI.
- Blood samples will be collected for:
 - Safety: CBC with differential, creatinine and ALT
 - Immunological assays: refer to Section 8.2.3 'Immunology Laboratory Evaluations'

- Participants will be asked to verify and confirm their telephone contact information at this time, and the importance of maintaining contact and following study procedures will be re-emphasized.

Following CHMI, participants will remain at the clinical center for an observation period of at least 30 minutes. This will allow the study team to confirm that there are no immediate reactions in response to injection of PfSPZ Challenge (7G8) and to provide immediate care if any reactions do occur. After the 30-minute observation period, an assessment will be performed including the measurement of temperature, pulse rate, and blood pressure, local and systemic reactions from PfSPZ Challenge. Participants will be instructed to contact the clinical investigator if they experience any medical problems.

Participants will be instructed on the symptoms of malaria and complications of malaria to include, but not limited to, fever (oral temperature of $\geq 38^{\circ}\text{C}$ [$\geq 100.4^{\circ}\text{F}$]), subjective fever, chills, rigors (shaking chills), sweats, cough, headache, dizziness, malaise/fatigue, arthralgia, myalgia, nausea, vomiting, abdominal pain, diarrhea, chest pain, shortness of breath, palpitations. Participants will be assessed for signs and symptoms of malaria from +7 days post CHMI through +28-day post CHMI or until the participant becomes parasitemic, is treated and is asymptomatic.

Memory Aid

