8.1.6 POST-CHMI FOLLOW-UP VISITS

8.1.6.1 +7 THROUGH +18 DAYS POST-CHMI

To facilitate daily close monitoring of clinical status and malaria diagnostics, all participants who underwent CHMI will be seen daily at the CVD starting + 7 days after CHMI until + 18 days after CHMI or until the participant finishes his/her anti-malarial treatment. Participants will be required to remain vigilant about maintaining lines open for rapid communication with the study team. A study physician will be available for consultation 24 hours per day.

The following will occur at each visit:

- Vital signs will be recorded.
- Medical history, AEs, SAEs and concomitant medication update.
- Targeted physical exam (if indicated).
- Participants will be assessed for signs and symptoms of malaria as mentioned in Section 8.3.1.2 "Malaria Events". Signs and symptoms of malaria infection will be collected on the visit CRF specific to CHMI follow-up and will not be considered as adverse events.
- Unsolicited AEs will be recorded through 28 days post-CHMI.
- Collection of blood samples for qRT-PCR.

- Symptomatic study participants may have blood samples for qRT-PCR collected as frequently as every 6-8 hours or at any time post-CHMI based upon the clinical judgment of the investigator
- Blood collection for qRT-PCR will be discontinued upon malaria diagnosis and treatment.
- The clinical center will have the capability to prepare and read TBS. (See Section 8.2.3.5 'Thick Blood Smear (TBS)').

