8.1.6.2 MANAGEMENT AND TREATMENT OF MALARIA PARASITEMIC PARTICIPANTS

Malaria infection will be treated when the criterion for a case is met. The case definition in this protocol identifies cases of malaria before gametocytes can develop. Detection of 2 positive qRT-PCR results at any level of parasitemia from samples collected \geq 12 hours apart will constitute a diagnosis of malaria. In the case of an acutely ill participant for whom the site PI (or designee) determines rapid diagnosis should be implemented, TBS may be utilized for diagnosis. If diagnosed, the study participant will be called to return to the clinical center to receive treatment. After completion of treatment participants will be asked to return to the clinical center +28 days post-CHMI.

- Safety laboratories will be drawn at time of diagnosis and at any other time point post-CHMI when deemed clinically indicated by the investigator.
- Just prior to the first dose of antimalarial medication, samples for preparation of TBS (to be read retrospectively) and confirmatory PCR will be collected.

All participants who develop blood-stage malaria infection will be treated with a standard dose of Malarone® (250 mg atovaquone/100 mg proguanil tablets) 4 tablets once per day for 3 days, as first line therapy. This will be done by directly observed treatment (DOT); that is, a study team physician or nurse will witness the swallowing of the Malarone® dose by the participant. In the event that a participant is allergic to, or unable to tolerate Malarone®, he or she will be treated with Coartem® (artemether/lumefantrine 20/120 tablets), an alternative, but equally effective, antimalarial agent; the adult dose for Coartem is 4 tablets orally twice daily for 3 days, with the first two doses on the day of parasitemia to be administered approximately 8 hours apart. The first dose each day will be administered by DOT whereas the second dose each day can be self-administered by the participant. Participants will be reminded of the potential side effects of the antimalarial treatment. All participants exposed to malaria will be unable to donate blood for 3 years.

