If symptoms develop, provided there are no contraindications, participants may be given acetaminophen or ibuprofen. In case of vomiting, particularly if it interferes with the administration of antimalarial medication, participants can be treated with prochlorperazine or ondansetron. Antimalarial medication administration will be repeated once if vomiting occurs within 30 minutes of initial administration. If vomiting occurs twice, an alternative antimalarial treatment will be selected (see above).

8.1.6.3 +20, +22 AND +25 DAYS POST-CHMI

Participants who remain negative for patency +18 days post-CHMI will be followed and evaluated during visits that occur +20, +22, and +25 days after CHMI. The evaluation of participants will include:

- Vital signs, medical history, concomitant medication, AEs, SAEs update, collection of unsolicited AEs and directed physical exam (if indicated)
- qRT-PCR

- Solicited signs and symptoms of malaria
- Safety labs may be drawn if clinically indicated.

Any participants who develop blood-stage malaria infection as measured by qRT-PCR will be treated as outlined above.

8.1.6.4 +28 DAYS POST-CHMI

This follow-up visit shall include:

- Vital signs, medical history, concomitant medication, AEs, SAEs update, collection of unsolicited AEs and directed physical exam (if indicated)
- qRT-PCR
- Solicited signs and symptoms of malaria
- CBC with differential, ALT and creatinine
- Immunology Assays: Refer to Section 8.2.3 'Immunology Laboratory Evaluations'

Any participants who develop blood-stage malaria infection as measured by qRT-PCR at this visit will be treated as outlined above.

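### The protocol disagrees with itself on whether treated participants have the day-28 qPCR; a site following the schedule footnote would take no scheduled parasite test from them after treatment

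*Combined protocol and SAP*

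**What the plan says.** Texts that limit the day-28 sample to participants who are still negative:

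- Section 1.3, footnote 5 under both the 3-week and the 12-week schedule: "qPCR will be performed 28 days post CHMI if subject remains malaria negative", followed by "Blood draw for qPCR will be discontinued upon malaria diagnosis and treatment".
- Section 8.2.3.4, in the sentence that sets the sampling days: days 20, 22, 25 and 28 are all tied to remaining negative.
- Section 10.1.3, Table 14 note c: the same limit for the same four days. Treated participants are to attend for three days of observed therapy and then on day 28, with no qPCR named.

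Texts that include everyone:

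- Section 2.2.3, among the precautions against CHMI risk: a "confirmatory negative PCR will be documented on all participants at Day 28 post CHMI".
- Section 8.2.3.4, last sentence: a final sample from every participant when surveillance closes on day +28.
- Section 8.1.6.4, the procedure list for the +28 visit: qRT-PCR appears with no restriction. Section 8.1.6.3, just before it, is limited to negatives.

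Treated participants do attend that visit. Section 8.1.6.2 says "After completion of treatment participants will be asked to return to the clinical center +28 days post-CHMI".

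**The concern.** Healthy volunteers are infected on purpose, and 2.2.3 presents a documented negative PCR at day 28 as one of the protections they receive. Clinic staff usually work from the schedule table, and its footnote carries the restrictive rule. If they follow it, the test that would confirm cure is done only in people never found infected and is omitted in those who were.

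What could be missed is a treatment failure without symptoms. No later scheduled test would find it: the smear and confirmatory PCR samples in 8.1.6.2 are drawn before the first antimalarial dose, and the day +56 visit (8.1.6.5) lists no parasite test and has a blood volume of 0 mL in the schedule.

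**Working it through.** **1. The rules side by side**

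| Place | Day-28 qPCR in a treated participant |
|---|---|
| 1.3, footnote 5 (both schedules) | No |
| 8.2.3.4, sampling-day sentence | No |
| 10.1.3, Table 14 note c | No (a payment note, so secondary) |
| 2.2.3 | Yes, explicitly |
| 8.2.3.4, last sentence | Yes, explicitly |
| 8.1.6.4 | Yes, because no restriction is stated |

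Section 8.2.3.4 falls on both sides, so citing it does not settle the matter. Reading the 2.2.3 sentence as covering only those still negative is strained, because the sentence after it uses the same description of participants for the day-56 visit, which everyone attends.

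Section 8.1.6.1 also says "Blood collection for qRT-PCR will be discontinued upon malaria diagnosis and treatment". That section governs the +7 to +18 visits only, and day +28 has its own section, so this stop rule is not part of the conflict.

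**2. Is the sample already planned for?** Day +28 blood volume in the schedule: CBC 4 + chemistry 8.5 + serum 25 + qPCR 2 = 39.5 mL, the printed total. Without the qPCR it would be 37.5 mL. The draw is therefore already counted.

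**3. How many participants does the conflict touch?** Planning rates from 9.2: 12 of 13 controls and 20 of 39 vaccinees infected, after eight dropouts. The 10/12 heterologous protection in the earlier German trial comes from 2.1.5.1.

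- Planning rates, eight dropouts: 12 + 20 = 32; 32/52 = 61.5%.
- Planning rates, no dropouts: 15 × 12/13 + 45 × 20/39 = 13.85 + 23.08 = 36.9, about 37 of 60 (61.5%).
- 10/12 protection, eight dropouts: 12 + 39 × 2/12 = 18.5, about 19 of 52 (36%).
- 10/12 protection, no dropouts: 13.85 + 45 × 2/12 = 21.3, about 21 of 60 (36%).
- If 2.2.3 and 8.1.6.4 are followed instead: none.

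**4. Nominal time from last Malarone dose to day +28** (three daily doses, 8.1.6.2)

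- Earliest: treatment starts on day 7 after a single high reading (4.1, item 19), last dose day 9, 28 − 9 = 19 days. If two positives on days 7 and 8 are needed, it is 18 days.
- Latest on past experience: first positive day 17 (2.2.1.3), second positive day 18, last dose day 20, 28 − 20 = 8 days.

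The +28 visit appears to have a window of ±7 days, although the columns of that row are imperfectly aligned in the text. On that reading, 8 to 19 days becomes about 1 to 26 days (8 − 7 and 19 + 7).

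**The case against.** The strongest reply is that the protocol can be read as requiring the test. Three places require or list it, the schedule already counts the 2 mL, Table 14 is a payment table, and the final sentence of 8.2.3.4 can serve as the exception to the stop rule just before it. Much of this stands. What it does not remove is footnote 5 in both schedules and the sampling-day clause of 8.2.3.4, which restrict day 28 in so many words.

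A second reply is that little would be lost. This also largely stands. Under 8.1.5, symptoms are followed for 28 days "or until the participant becomes parasitemic, is treated and is asymptomatic", and they are solicited again at +28 (8.1.6.4). Under 8.1.6.1, "Symptomatic study participants may have blood samples for qRT-PCR collected as frequently as every 6-8 hours or at any time post-CHMI". First-line Malarone is given under direct observation. Section 3.1 gives parasite growth of about 10-fold every two days, so a failing infection should not stay low for long. The remark in 8.2.3.4 that treatment guided by qPCR almost always precedes symptoms concerns first detection; it does not show that a treatment failure would stay silent.

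A reader might infer three stronger things that the documents do not support:

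- *That treated participants are left without follow-up.* Symptom review, unscheduled qPCR and the +28 and +56 visits all remain.
- *That 32 of 52 measures harm.* It counts people covered by conflicting instructions. The documents give no treatment-failure rate, so missed failures cannot be computed.
- *That the efficacy result is at risk.* A treated participant has already been counted as infected.

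**Conclusion.** The conflict is real and stands in the current text, but it is minor. If a site follows footnote 5, every treated participant goes without a scheduled parasite test after treatment, and the safeguard in 2.2.3 covers only those never found infected. That is 32 of 52 at the planning rates and about 19 of 52 at 10/12 protection. If it follows 2.2.3 and 8.1.6.4, nobody is affected. Expected harm is low, on the assumption that failure is rare under observed dosing. The counts assume the 9.2 dropout and infection figures, or the German trial's rate in vaccinees. The 8 to 19 days is nominal and moves with the visit window. An edit is needed whichever rule the sponsor intends, because keeping the restriction would mean amending 2.2.3, 8.1.6.4 and the end of 8.2.3.4.

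**What to change.** - **Footnote 5, both schedules:** replace the last two sentences with: *Scheduled qPCR stops once treatment begins; a final 2 mL qPCR is drawn at day +28 from all participants, including those treated.*
- **8.2.3.4:** limit the still-negative condition to days 20, 22 and 25. Align **Table 14 note c**.
- **8.1.6.4:** the existing line, "Any participants who develop blood-stage malaria infection as measured by qRT-PCR at this visit will be treated as outlined above", points back to 8.1.6.2, which gives Malarone first and would repeat it after a suspected Malarone failure. Add that a positive day-28 qPCR in a previously treated participant prompts a repeat sample at least 12 hours later (matching the two-sample case definition) and a clinical evaluation. A confirmed failure is then treated with the alternative antimalarial, not the drug already given.
- **Late diagnoses:** if treatment is not complete by day +28, take the final sample after it ends.

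The cost is about 19 to 37 assays (18.5 and 36.9 in the working), at a visit treated participants already attend and with the 2 mL already counted, plus an occasional repeat sample. Sample size and the efficacy analysis do not change.
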